12.2 Patient Reported Outcome (PRO-2)

The PRO-2 is calculated based on the sum of the weighted patient-reported subscores of CDAI for liquid or soft stool frequency [SF] plus abdominal pain [AP] in the 7 days prior to the study visit. PRO-2 is calculated (as in the CDAI) by adding the values of the

summed stool frequency scores multiplied by 2 plus the summed abdominal pain scores multiplied by 5.

The SF and AP score at an assessment visit will be the average of the daily values reported during the 7 days preceding the scheduled assessment visit.

- If 7 days daily values are not available, an average will be calculated based on the number of days with available data as follows:
 - An average for the most recent 6 days will be calculated if data for only 6 days are available,
 - An average for the most recent 5 days will be calculated if data for only 5 days are available,
 - An average for the most recent 4 days will be calculated if data for only 4 days are available.
- If the minimum number of days of diary data (i.e., 4 days for SF and AP) are not available, then the subject's score for that visit will be considered missing and NRI will be used for any endpoints (e.g., clinical remission) relating to data for this visit. Subjects who discontinue prior to the endpoint for any reason will be considered as "not achieved" for the endpoint.

12.3 Crohn's Disease Endoscopic Index of Severity (CDEIS)

Scoring System for Crohn's Disease Endoscopic Index of Severity (CDEIS)

	Rectum	Sigmoid and Left Colon	Transverse Colon	Right Colon	Ileum	Total
Deep ulcerations (12 if present)						Total 1
Superficial ulcerations (6 if present)						Total 2
Surface involved by disease (cm)						Total 3
Surface involved by ulcerations (cm)						Total 4
			Total 1 + Total 2 + Total 3 + Total 4 =			Total A
		Number of segments totally or partially explored				N
			Total A/n =			Total B
		If an ulcerated stenosis is present anywhere add 3 =				C
		If a nonulcerated stenosis is present anywhere add 3 =				D
			Total B + C + D =			CDEIS

If deep ulceration is present the value is 12. Sum the present values for rectum, sigmoid and left colon, transverse colon, right colon and ileum.

If superficial ulceration is present the value is 6. Sum the present values for rectum, sigmoid and left colon, transverse colon, right colon and ileum.

Sum the surface involved by the disease (cm from 0 – 10) for rectum, sigmoid and left colon, transverse colon, right colon and ileum. The sum has one decimal place.

Sum the surface involved by ulcerations (cm from 0 – 10) for rectum, sigmoid and left colon, transverse colon, right colon and ileum. The sum has one decimal place.

A is the sum of the sum for deep ulceration + sum for superficial ulceration + sum for surface involved by disease + sum for surface involved by ulceration.

n is the number of segments totally or partially explored.

B is A/n.

C if ulcerated stenosis is present anywhere add 3.

D if non ulcerated stenosis is present anywhere add 3.

The total score (CDEIS) is the sum of the sum for deep ulceration + sum for superficial ulceration + sum for surface involved by disease + sum for surface involved by ulceration (for all examined segments) divided by the number of segments totally or partially explored + 3 if an ulcerated stenosis present (> 0) + 3 if a non-ulcerated stenosis present (> 0).

Please use baseline CDEIS score for the disease location (pattern) analysis:

- a. Ileum only: at least one component score > 0 in ileum and all component scores = 0 in colon (left, transverse, right, sigmoid, rectum)
- b. Colonic only: all component scores = 0 in ileum and at least one component score > 0 in colon (left, transverse, right, sigmoid, rectum)
- c. Ileocolonic: at least one component score > 0 in ileum and at least one component score > 0 in colon (left, transverse, right, sigmoid, rectum)

The following convention applies to Crohn's Disease Endoscopic Index of Severity (CDEIS):

If any item among the explored segments is missing, then set the total score to missing.

12.4 Simple Endoscopic Score – CD (SES-CD)

SES-CD is calculated based the sum of individual segment values for four endoscopic variables (presence and size of ulcers, ulcerated surface, affected surface and presence of narrowing). Each variable in each segment be scored 0 to 3 resulting in SES-CD values ranging from 0 to 56 with higher scores indicating more severe disease.

Variable	Score			
	0	1	2	3
Size of ulcers (cm)	None	Aphthous ulcers (diameter 0.1–0.5)	Large ulcers (diameter 0.5–2)	Very large ulcers (diameter >2)
Ulcerated surface (%)	None	<10	10–30	>30
Affected surface (%)	Unaffected segment	<50	50–75	>75
Presence of narrowings	None	Single, can be passed	Multiple, can be passed	Cannot be passed

*Total SES-CD: sum of the values of the 4 variables for the 5 bowel segments. Values are given to each variable and for every examined bowel segment (for example, rectum, left colon, transverse colon, right colon and ileum).

Medscape

Source: Nat Rev Gastroenterol Hepatol ©2009 Nature Publishing Group

SES-CD Scoring:

	Rectum	Sigmoid and Left Colon	Transverse Colon	Right Colon	Ileum	Total
Size of Ulcers Enter: 0 if none 1 if aphthous ulcers (Ø 0.1 to 0.5 cm) 2 if large ulcers (Ø 0.5 to 2 cm) 3 if very large ulcers (Ø > 2 cm)						
Ulcerated Surface Enter: 0 if none 1 if < 10% 2 if 10% – 30% 3 if > 30%						
Affected Surface Enter: 0 if unaffected segments 1 if < 50% 2 if 50% – 75% 3 if > 75%						
Presence of Narrowing Enter: 0 if none 1 if single, can be passed 2 if multiple, can be passed 3 if cannot be passed						
					TOTAL =	

The following convention applies to Simple Endoscopic Score – CD (SES-CD) total score:

[figure not shown]
- Baseline missing variables are imputed as 0
- Post-baseline total score will be missing if > 8 individual variables are missing. Otherwise, missing variables will be imputed as 0.

The following convention applies to Simple Endoscopic Score – CD (SES-CD) subscore (Size of Ulcers, Ulcerated Surface, Affected Surface, Presence of Narrowing) if the endpoint is only related to the subscores:

- Baseline missing variables in any subscore are imputed as 0
- Post-baseline subscore will be missing if > 2 individual variables for this subscore are missing. Otherwise, missing variables for this subscore will be imputed as 0.

12.5 Inflammatory Bowel Disease Questionnaire (IBDQ)

The IBDQ is a 32-item (ranges 1 – 7) self-report questionnaire for patients with IBD to evaluate the patient reported outcomes across 4 domains: bowel symptoms (loose stools, abdominal pain), systemic symptoms (fatigue, altered sleep pattern), social function (work attendance, need to cancel social events), and emotional function (anger, depression, irritability), as shown in the figure below. The IBDQ total score ranges from 32 to 224 with a higher score indicating better outcome.

The derivation of the IBDQ total score and the four IBDQ domain scores are as follows:

Domain Scores:

- S1. BOWEL SYMPTOM: $Q1 + Q5 + Q9 + Q13 + Q17 + Q20 + Q22 + Q24 + Q26 + Q29$
[score ranges from 10 - 70],
- S2. SOCIAL FUNCTION: $Q4 + Q8 + Q12 + Q16 + Q28$
[score ranges from 5 - 35],
- S3. SYSTEMIC SYMPTOM: $Q2 + Q6 + Q10 + Q14 + Q18$
[score ranges from 5 - 35],
- S4. EMOTIONAL FUNCTION: $Q3 + Q7 + Q11 + Q15 + Q19 + Q21 + Q23 + Q25 + Q27 + Q30 + Q31 + Q32$
[score ranges from 12 - 84].

Total Score:

IBDQ Total Score = SUM of (bowel symptom domain score, social function domain score, systemic symptom domain score, emotional function domain score).

The following convention applies to Inflammatory Bowel Disease Questionnaire (IBDQ):

When not more than 20% of items in a domain of IBDQ were missing, it was substituted with the mean values from the items completed in the particular domain; otherwise, they were treated as missing. The 20% threshold in each domain is: bowel symptom domain: 2 items, systemic symptom domain: 1 item, social function domain: 1 item, emotional function domain: 2 items. If any of the 4 domain scores is missing, the total IBDQ score will be set to missing.

12.6 Isolated Ileitis

- For isolated ileitis in the analysis using CDEIS: Patients who have CDEIS = 0 in all segments other than ileum are considered to have isolated ileitis.
- For isolated ileitis in the analysis using SESCD: Patients who have SESCD = 0 in all segments other than ileum are considered to have isolated ileitis.

12.7 Area of Safety Interest (ASI)

ASI Grouping	Categories (ASI)	Search Criteria	Terms to Display	Include in AE Overview (Y/N)
Adjudicated CV Events	MACE	Adjudicated terms will be identified using CECAT and CETERM from the CE SDTM dataset.	Display underlined terms defined by the following adjudicated terms: 
 • CV Death which includes adjudicated results of: Sudden Cardiac death, Death due to Acute MI, Death due to Heart Failure, Death due to CV Procedures, Death due to CV Hemorrhage, Death due to Other CV Causes (specify), Undetermined Death, fatal stroke (ischemic, hemorrhagic, undetermined) • Myocardial infarction • Stroke: Ischemic stroke, Hemorrhagic stroke, Undetermined stroke 	Y
	Extended MACE	Adjudicated terms will be identified (for MACE +) using CECAT and CETERM from the CE SDTM dataset.	Display underlined terms from MACE and underlined terms below: 
 • Hospitalization for Unstable Angina • PCI • CABG 	N
Serious infections, TB, fungal and opportunistic infections (including herpes zoster)	Serious infections	Infections and Infestations SOC	PTs	Y
	TB	Tuberculosis (including Investigations) CMQ (code 80000033)	PTs	Y
	Opportunistic infections	Opportunistic infections CMQ (code 80000073)	PTs	Y
	Fungal infections	Fungal infections CMQ (code 80000063)	PTs	N
	Herpes Zoster	Herpes zoster CMQ (code 80000175)	PTs	N

ASI Grouping	Categories (ASI)	Search Criteria	Terms to Display	Include in AE Overview (Y/N)
Malignancies	All possible malignancies	Narrow Malignancies (SMQ 20000090)	PTs	N
	Malignant Tumors	Narrow Malignant tumors (SMQ 20000194)	PTs	Y
	Non-melanoma skin cancer (NMSC)	Broad Skin malignant tumors (SMQ 20000204) excluding terms identified by the Melanoma CMQ (code 80000119)	PTs	N
	Malignancies excluding NMSC	'Malignancies excluding NMSC' is identified by the 'Malignant Tumours' search excluding terms identified by the 'Non-melanoma skin cancer' (NMSC) search.	PTs	Y
Hypersensitivity Reaction	Hypersensitivity	Narrow Hypersensitivity (SMQ 20000214)	PTs	Y
	Anaphylactic Reaction	Narrow Anaphylactic reaction (SMQ 20000021)	PTs	Y

ASI Grouping	Categories (ASI)	Search Criteria	Terms to Display	Include in AE Overview (Y/N)
Hepatic Event	Hepatic Event	Broad Hepatic failure, fibrosis and cirrhosis and other liver damage-related conditions (SMQ 20000013) Broad Hepatitis, non infectious (SMQ 20000010) Broad Cholestasis and jaundice of hepatic origin (SMQ 20000009) Broad Liver related investigations, signs and symptoms (SMQ 20000008) Narrow Liver-related coagulation and bleeding disturbances (SMQ 20000015)	PTs	N

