5.2.2 Assessment of adverse events

5.2.2.1 Definitions of adverse events

Adverse event

An adverse event (AE) is defined as any untoward medical occurrence in a patient or clinical investigation subject administered a medicinal product and which does not necessarily have to have a causal relationship with this treatment. An AE can therefore be any unfavorable and unintended sign (including an abnormal laboratory finding), symptom or disease temporally associate with the use of a medicinal (investigational) product, whether or not the event is considered causally related to the use of the product.

Such an event can result from use of the drug as stipulated in the protocol or labeling, as well as from accidental or intentional overdose, drug abuse, or drug withdrawal. Any worsening of a pre-existing condition or illness is considered an AE. Laboratory abnormalities and changes in vital signs are considered to be AEs only if they result in discontinuation from the study drug, necessitate therapeutic medical intervention, and/or if the investigator considers them to be AEs.

An elective surgery/procedure scheduled to occur during a study will not be considered an adverse event if the surgery/procedure is being performed for a pre-existing condition and the surgery/procedure has been pre-planned prior to study entry. However, if the pre-existing condition deteriorates unexpectedly during the study (e.g., surgery performed earlier than planned), then the deterioration of the condition for which the elective surgery/procedure is being done will be considered an adverse event.

Adverse reaction

An adverse reaction is defined as a response to a medicinal product which is noxious and unintended. Response in this context means that a causal relationship between a medicinal product and an adverse event is at least a reasonable possibility. Adverse reactions may arise from use of the product within or outside the terms of the marketing authorisation or from occupational exposure. Conditions of use outside the marketing authorization include off label use, overdose, misuse, abuse and medication errors.

Serious adverse event

A serious adverse event (SAE) is defined as any AE which results in death, is life-threatening, results in persistent or significant disability or incapacity, requires inpatient hospitalisation or prolongation of existing hospitalisation, is a congenital anomaly / birth

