3.0 Introduction

This statistical analysis plan (SAP) describes the statistical analyses to be completed by the Data and Statistical Science Department for ABBV-066 Study M15-989. It provides details to further elaborate statistical methods as outlined in the protocol and describes analysis conventions to guide the statistical programming work.

Unless noted otherwise, all analyses will be performed using SAS version 9.2 or later (SAS Institute Inc., Cary, NC 27513) under the UNIX operating system.

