4.2 Study Design

This open label long term extension trial investigates the long-term safety and efficacy of BI 655066/ABBV-066 (risankizumab). Approximately 60 patients who met the entry criteria were planned for inclusion in this trial, rolling over from preceding trial Study M15-993/1311.6.

[figure not shown]
All patients directly rolled over from Study M15-993/1311.6 into Study M15-989/1311.20 received 180 mg BI 655066/ABBV-066 (risankizumab) subcutaneously (SC) from Visit 2 onwards every 8 weeks. Patients who lost clinical response or remission after the end of treatment in Study M15-993/1311.6 and/or at screening for Study 1311.20/M15-989 received open label, i.e., re-induction treatment with three intravenous infusions (IV) of 600 mg each every 4 weeks. Patients who complete this study may elect to continue in Study M16-000 Sub-Study 3 (Phase 3 open label extension study).

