10.2.1.6 Areas of Safety Interest

The Areas of Safety Interest (ASI) categories are listed in Appendix [12.7](#). These will be summarized and presented using primary MedDRA query and MedDRA PT.

Additional ASIs may be considered for tabulation/summary based on recommendations from Clinical and Safety teams, as deemed appropriate.

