10.2.2 SAEs (Including Deaths) and Adverse Events Leading to Study Drug Discontinuation

The number and percentage of subjects experiencing treatment-emergent SAEs and adverse events leading to discontinuation of study drug will be tabulated according to the primary MedDRA SOC and PT for each treatment group.

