10.2.3 Listing of Adverse Events

The following summaries of AEs will be prepared.

- Listing of Subjects with Treatment-Emergent Adverse Events of Special Interest
- Listing of Subjects with Treatment-Emergent Serious Adverse Events
- Listing of all adverse events that led to discontinuation of study drug.
- Listing of all deaths.

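### Does the serious-infections row in SAP 12.7 leave open whether non-serious infections are counted?

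*SAP*

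**What the plan says.** SAP 10.2.1.6 sends the reader to Appendix 12.7 for the categories of safety interest and says of them: "These will be summarized and presented using primary MedDRA query and MedDRA PT". In 12.7 each category has a grouping, a category label, search criteria, terms to display, and a yes/no for inclusion in the adverse event overview.

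The row in question belongs to a grouping whose label begins "Serious infections, TB, fungal and opportunistic infections (including herpes zoster". Its category label is serious infections, its search cell is "Infections and Infestations SOC", it displays preferred terms, and it is marked for the overview.

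Three other places bear on it:

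- Protocol 5.2.2.1 defines seriousness at event level: "A serious adverse event (SAE) is defined as any AE which results in death", followed by the remaining criteria.
- SAP 10.2.2 gives the number and percentage of subjects for whom "treatment-emergent SAEs and adverse events leading to discontinuation of study drug will be tabulated according to the primary MedDRA SOC and PT".
- SAP 10.2.3 includes a "Listing of Subjects with Treatment-Emergent Serious Adverse Events".

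Protocol 7.3.3 names drug-related adverse events and serious infection as the primary focus of the safety evaluation.

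**The concern.** The search column looks like the selection rule, and in this row it contains no seriousness condition. A MedDRA SOC is a set of terms, while seriousness belongs to the individual event, so naming the SOC cannot by itself restrict the row to serious events. SAP 3.0 says the document "describes analysis conventions to guide the statistical programming work". A programmer who worked from the search cell alone would select all treatment-emergent infections and print them under a heading that says serious.

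Were that to happen, the row for a named safety focus would be inflated, and so would its contribution to the adverse event overview. The difference might not be trivial, because Protocol 1.2 lists nasopharyngitis and upper respiratory tract infection among the most frequent adverse events with risankizumab.

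**Working it through.** There is no planned figure to reproduce. The check is a reading of the row against the rest of the plan, with one small calculation.

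**1. Where the row sits.** SAP 12.7 has 2 adjudicated cardiovascular + 5 infection + 4 malignancy + 2 hypersensitivity + 1 hepatic = 14 categories. Serious infections is the only one of the 14 whose label adds an event-level condition that its search and display cells do not state. The other 4 infection rows (TB, opportunistic, fungal, herpes zoster) are not limited to serious events, and their labels do not say they are.

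**2. What the cells mean together.** There are two candidate readings:

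| Reading | Events selected | Consistent with the category label? |
|---|---|---|
| Label and term set together | serious treatment-emergent events in the infections SOC | yes |
| Search cell alone | all treatment-emergent events in that SOC | no |

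The second reading requires ignoring the name of the category being produced. Only the first uses every cell of the row. It also needs nothing that the plan lacks: seriousness is defined in Protocol 5.2.2.1, and SAP 10.2.2 already relies on it.

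**3. Silence elsewhere.** SAP 10.2.1.1, 10.2.1.6, 10.2.2 and 10.2.3 do not mention serious infection. They do not name any of the other 13 categories either; the detail is left to 12.7. The restriction to treatment-emergent events works the same way. No search cell states it, and it comes from the general rules in 10.2.1.

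**4. Is the information available without this row?** Yes. SAP 10.2.2 tabulates treatment-emergent serious events by primary SOC and preferred term, so its infections SOC line gives the number of subjects with a serious infection. SAP 10.2.3 lists subjects with serious events. SAP 10.2.1.2 tabulates all treatment-emergent events by SOC, which gives the count for all infections.

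**5. Size if the flag were forgotten.** SAP 4.2 says: "Approximately 60 patients who met the entry criteria were planned for inclusion in this trial". Taking 60 as denominator, each subject whose only treatment-emergent infections were non-serious would add 100 × 1/60 = 1.67, or about 1.7 percentage points. A treatment group with fewer subjects would give each one more weight. The documents give no infection rates, so the number of such subjects cannot be estimated. If the row is programmed as labelled, the change is 0.

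**6. Would the mistake be seen?** An unfiltered row would reproduce the all-infections count of 10.2.1.2 and exceed the infections line of 10.2.2 whenever any subject had only non-serious infections. It could even exceed the overview's own line for any treatment-emergent serious event, which is impossible for a correctly filtered row.

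**The case for a change.** The strongest case for the concern is the table's own practice. Other rows write their limits into the search cell: narrow or broad query scope, the exclusion of melanoma terms, the exclusion of non-melanoma skin cancer, and the adjudicated source for the cardiovascular rows. Set beside those, a bare SOC name can look like a deliberate choice to take everything in it. The row also feeds the overview and concerns a named safety focus, and adding one word would cost almost nothing.

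The observation about the wording stands: the condition appears in the grouping and category labels and not in the search cell. The inference from it does not. The scope and exclusion entries operate on sets of terms, which is what a search cell is for, whereas seriousness is a flag on the event record. This distinction is not absolute, because the cardiovascular rows do name a record source in that column. Even so, uneven placement of conditions across rows does not cancel a condition printed in the category name. That the edit would be cheap does not show that the plan is wrong without it.

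**Conclusion.** The concern does not hold. Label and term set together define the row as serious treatment-emergent events in the infections SOC, and an analyst who follows the plan gets the right count. The effect on any result is nil under that reading. The 1.7 percentage points per subject belongs only to a programming slip that contradicts the row's own name and that the table in SAP 10.2.2 would expose. No hypothesis test or primary endpoint depends on the row (Protocol 5.2.1 and 7.2).

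This rests on two assumptions: that the category label is read as part of the row's definition, and that SOC membership in 12.7 means primary SOC, as in 10.2.1.2 and 10.2.2. Both are the ordinary reading of the SAP.

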12.8 Common Toxicity Criteria (CTC) Grade for Laboratory Data

Test	Grade 1	Grade 2	Grade 3	Grade 4
Chemistry Variables				
SGPT/ALT increased	> ULN – 3.0 × ULN	> 3.0 – 5.0 × ULN	> 5.0 – 20.0 × ULN	> 20.0 × ULN
SGOT/AST increased	> ULN – 3.0 × ULN	> 3.0 – 5.0 × ULN	> 5.0 – 20.0 × ULN	> 20.0 × ULN
GGT increased	> ULN – 2.5 × ULN	> 2.5 – 5.0 × ULN	> 5.0 – 20.0 × ULN	> 20.0 × ULN
ALP increased	> ULN – 2.5 × ULN	> 2.5 – 5.0 × ULN	> 5.0 – 20.0 × ULN	> 20.0 × ULN
TBL increased	> ULN – 1.5 × ULN	> 1.5 – 3.0 × ULN	> 3.0 – 10.0 × ULN	> 10.0 × ULN
Creatinine increased	> ULN – 1.5 × ULN	> 1.5 – 3.0 × ULN	> 3.0 – 6.0 × ULN	> 6.0 × ULN
CPK increased	> ULN – 2.5 × ULN	> 2.5 – 5.0 × ULN	> 5.0 – 10.0 × ULN	> 10.0 × ULN

Test	Grade 1	Grade 2	Grade 3	Grade 4
Chemistry Variables				
Total Cholesterol increased	> ULN - 7.75	> 7.75 - 10.34	> 10.34 - 12.92	> 12.92
Albumin decreased	< LLN - 30	< 30 - 20	< 20	N/A
Triglycerides increased	1.71 - 3.42	> 3.42 - 5.7	> 5.7 - 11.4	> 11.4
Glucose	< LLN - 3.0 or > ULN - 8.9	< 3.0 - 2.2 or > 8.9 - 13.9	< 2.2 - 1.7 or > 13.9 - 27.8	< 1.7 or > 27.8
Sodium	< LLN - 130 or > ULN - 150	> 150 - 155	< 130 - 120 or > 155 - 160	< 120 or > 160
Potassium	< LLN - 3.0 or > ULN - 5.5	< LLN - 3.0 or > 5.5 - 6.0	< 3.0 - 2.5 or > 6.0 - 7.0	< 2.5 or > 7.0
Calcium	< LLN - 2.0 or > ULN - 2.9	< 2.0 - 1.75 or > 2.9 - 3.1	< 1.75 - 1.5 or > 3.1 - 3.4	< 1.5 or > 3.4
Hematology Variables				
Hemoglobin decreased	< LLN - 100.0 g/L	< 100.0 - 80.0 g/L	< 80.0 g/L	N/A
Neutrophil count decreased	< LLN - $1.5 \times 10^9/L$	< 1.5 - $1.0 \times 10^9/L$	< 1.0 - $0.5 \times 10^9/L$	< $0.5 \times 10^9/L$
WBC decreased	< LLN - $3.0 \times 10^9/L$	< 3.0 - $2.0 \times 10^9/L$	< 2.0 - $1.0 \times 10^9/L$	< $1.0 \times 10^9/L$
Lymphocyte count decreased	< LLN - $0.8 \times 10^9/L$	< 0.8 - $0.5 \times 10^9/L$	< 0.5 - $0.2 \times 10^9/L$	< $0.2 \times 10^9/L$
Platelets count decreased	< LLN - $75.0 \times 10^9/L$	< 75.0 - $50.0 \times 10^9/L$	< 50.0 - $25.0 \times 10^9/L$	< $25.0 \times 10^9/L$

